# 5.5 PHARMACOKINETIC, PHARMACODYNAMIC AND PHARMACOGENOMIC / PHARMACOGENETIC

## 5.5.1 Pharmacokinetic Analyses

Not applicable.

#### 5.5.2 Pharmacodynamic Analyses

A PD analysis plan will be defined and reported separately.

## 5.5.3 Biomarker Analyses

A biomarker analysis plan will be defined and reported separately

#### 5.5.4 Pharmacogenomic/Pharmacogenetic Analyses

A pharmacogenomic analysis plan will be defined and reported separately.

#### 5.6 SAFETY ANALYSES

All safety analyses will be performed on the Safety Analysis Set. The incidence of AEs (including changes from baseline in physical examination), out-of-normal-range laboratory safety test variables, abnormal ECG findings, along with change from Baseline in laboratory safety test variables, ECGs, and vital sign measurements summarized yearly by treatment group using descriptive statistics.

#### **5.6.1** Extent of Exposure

Cumulative exposure to study drug will be summarized by the number and percentage of subjects (remaining in study) exposed to study drug in days or other time units by treatment group. In addition, the number of days or other time units of exposure will be summarized descriptively as a continuous variable. The average dose and relative dose intensity (actual dose administered divided by planned dose) will be summarized by month and overall study and by treatment group.

#### **5.6.2** Adverse Events

The AE verbatim descriptions (investigator terms from the CRF) will be classified into standardized medical terminology using the Medical Dictionary for Regulatory Activities (MedDRA - Version 16.0 or higher). AEs will be coded to the MedDRA lower level term (LLT) closest to the verbatim term. The linked MedDRA preferred term (PT) and primary system organ class (SOC) are also captured in the database.

All AEs observed during the study will be reported on the CRF. All AEs, regardless of relationship to study drug or procedure, should be collected beginning from the time the subject signs the study ICF through the end of the study and for a minimum of 30 days after the last dose. Serious AEs will be collected through the end of study, and for a minimum of 30 days after the last dose.

A treatment-emergent AE (TEAE) is defined as an AE that emerges during treatment, having been absent at pretreatment (Baseline) or

- Reemerges during treatment, having been present at pretreatment (Baseline) but stopped before treatment, or
- Worsens in severity during treatment relative to the pretreatment state, when the AE is continuous.

Only those AEs that were treatment emergent (including CEC adjudicated events) will be included in summary tables. All AEs, treatment emergent or otherwise, will be presented in subject data listings.

TEAEs will be summarized by treatment group on the Safety Analysis Set. The incidence of TEAEs will be reported as the number (percentage) of subjects with TEAEs by SOC and PT (these summaries will be done with and without CEC adjudicated events). A subject will be counted only once within a SOC and PT, even if the subject experienced more than one TEAE within a specific SOC and PT. The number (percentage) of subjects with TEAEs will also be summarized by maximum severity (mild, moderate, or severe). The number (percentage) of subjects with TEAEs will also be summarized by relationship to study drug (Yes = related, and No = Not related).

AEs will be summarized by the following subgroups: age (< 65 years,  $\geq$  65 years to <75 years,  $\geq$ 75 years), sex (male, female), race (white, black, other), presence of established CV disease or CV risk factors without established CV disease, pre-diabetes at Baseline, and T2DM at Baseline (with and without).

- The number (percentage) of subjects with TEAEs leading to death will be summarized by MedDRA SOC and PT for each treatment group. A subject data listing of all AEs leading to death will be provided.
- The number (percentage) of subjects with treatment-emergent SAEs will be summarized by MedDRA SOC and PT for each treatment group. A subject data listing of all SAEs will be provided.
- The number (percentage) of subjects with TEAEs leading to discontinuation from study drug will be summarized by MedDRA SOC and PT for each treatment group. A subject data listing of all AEs leading to discontinuation from study drug will be provided.
- The incidence of AEs of interest (Study Specific Events, see Section 9.5.4.4 of the protocol) will be summarized separately. In addition, for each AE of interest, Kaplan-Meier curves and median time to first event and 95% CI will be presented. The Safety Analysis Set will be used for this analysis.

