8.2 SECONDARY OBJECTIVES

Key Secondary Objective

- To confirm that, in subjects with prediabetes at Baseline based on the 2013 ADA guideline, lorcaserin HCl 10 mg BID reduces the incidence of conversion to T2DM compared to placebo (revised per Amendments 01 and 02)

Other Secondary Objectives (revised per Amendment 02)

MACE and MACE+ Related: (revised per Amendment 02)

- To determine whether the rates of the individual events comprising the MACE+ endpoints are different in subjects on lorcaserin compared to those on placebo
- To determine whether lorcaserin reduces all-cause mortality compared with placebo

Diabetes and Prediabetes Related: (revised per Amendment 02)

- To evaluate the effect of lorcaserin HCl 10 mg BID compared to placebo on conversion to normal glucose homeostasis at 1 year and yearly thereafter in subjects with prediabetes at Baseline (revised per Amendment 01)
- To evaluate whether in all subjects without any type of diabetes at Baseline, lorcaserin HCl 10 mg BID reduces the incidence of conversion to T2DM compared to placebo (revised per Amendment 01)
- To confirm that, in subjects with T2DM at Baseline, lorcaserin HCl 10 mg BID improves glycemic control (HbA_{1c}) compared to placebo at 6 months

Renal Related: (revised per Amendment 02)

- To evaluate the long-term effect of lorcaserin HCl compared to placebo on renal function in all subjects (revised per Amendment 01)
- To evaluate the long-term effect of lorcaserin HCl compared to placebo on renal function in subjects with T2DM at Baseline
- To evaluate the long-term effect of lorcaserin HCl compared to placebo on renal function in subjects with prediabetes at Baseline (revised per Amendment 02)

Safety Objectives (revised per Amendment 02)

- To evaluate echocardiographically determined cardiac valvular function and pulmonary arterial pressure changes associated with treatment with lorcaserin HCl 10 mg BID compared to placebo at 1 year
- To evaluate the long-term safety of lorcaserin HCl 10 mg BID

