9.5.1.5 Safety Assessments

Safety assessments will consist of monitoring and recording all AEs and SAEs; regular monitoring of hematology, blood chemistry, and urinalysis; periodic measurement of vital signs and electrocardiograms (ECGs); and performance of physical examinations. Additional safety assessments specific to this study will include echocardiography.

AES AND EVENTS ASSOCIATED WITH SPECIAL SITUATIONS (revised per Amendment 01)

An adverse event (AE) is any untoward medical occurrence in a subject or clinical investigation subject administered an investigational product. An AE does not necessarily have a causal relationship with the medicinal product. For this study, the study drug is lorcaserin HCl.

The criteria for identifying AEs are:

- Any unfavorable and unintended sign (including an abnormal laboratory finding), symptom, or disease temporally associated with the use of an investigational product, whether or not considered related to the investigational product
- Any new disease or exacerbation of an existing disease
- Any deterioration in nonprotocol-required measurements of a laboratory value or other clinical test (eg, ECG or x-ray) that results in symptoms, a change in treatment, or discontinuation of study drug
- Recurrence of an intermittent medical condition (eg, headache) not present pretreatment (Baseline)
- An abnormal laboratory test result should be considered an AE if the identified laboratory abnormality leads to any type of intervention, whether prescribed in the protocol or not.

A laboratory result should be considered by the investigator to be an AE if it:

- Results in the withdrawal of study drug
- Results in withholding of study drug pending some investigational outcome
- Results in an intervention, based on medical evaluation (eg, potassium supplement for hypokalemia)
- Results in any out-of-range laboratory value (Sponsor's Grading for Laboratory Value provided as reference in [Appendix 3](#)) that in the investigator's judgment fulfills the definitions of an AE with regard to the subject's medical profile (revised per Amendment 01)

All AEs observed during the study will be reported on the CRF. All AEs, regardless of relationship to study drug or procedure, should be collected beginning from the time the subject signs the study ICF through the end of the study. –(revised per Amendment 01)

MACE and MACE+ events and other study-specific AEs of interest will be followed until EOS. (revised per Amendment 01)

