- **New symptoms or worsening symptoms of valvular heart disease** (revised per Amendment 01)
- **New or worsening symptomatic pulmonary hypertension** (revised per Amendment 01)
- **Malignant neoplasms**, with the exception of basal cell and squamous cell carcinomas of the skin
- **Fibroadenomas of the breast or ductal carcinoma *in situ***

Additionally, the following additional study specific AEs of interest should be reported using the procedures detailed in Reporting of SAEs ([Section 9.5.4.1](#)), even if the study-specific event does not meet serious criteria. If the event meets seriousness criteria, it should be reported as an SAE as above. However, if the event listed below does not meet serious criteria, it should be noted as non-serious on the Adverse Event CRF: (revised per Amendment 01)

- **Suicidal ideation** (revised per Amendment 01)
- **Euphoria** (revised per Amendment 01)
- **Asymptomatic new onset or worsened valvular heart disease** as demonstrated by objective assessment, eg, echocardiography or cardiac catheterization. New onset valvular disease is defined as subjects who develop mild or greater aortic insufficiency and moderate or greater grading for all other valvular lesions (eg, mitral regurgitation, aortic stenosis) on imaging in subjects without any valvular disease at Baseline. Worsened valvular disease is defined in subjects who have existing FDA defined valvulopathy at Baseline increase in severity of regurgitation or stenosis as demonstrated by objective assessments (eg, imaging assessments such as magnetic resonance imaging [MRI], echocardiography, or cardiac catheterization). (revised per Amendment 01)
- **Asymptomatic new onset or worsened pulmonary hypertension** as documented by echocardiography or cardiac catheterization. New onset of pulmonary hypertension is defined as estimated pulmonary artery or right ventricular systolic pressure greater than

40 mmHg or mean pulmonary artery pressure equal-or-greater than 25 mmHg in the subjects without any pulmonary hypertension at Baseline. Worsening pulmonary hypertension is defined in subjects who have documented objective assessment pulmonary hypertension at Baseline as an increase in pulmonary artery systolic pressure, or mean artery pressure by more than 10 mmHg. (revised per Amendment 01)

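### For malignancy, the SAP does not say whether events after stopping drug count, plans a Kaplan-Meier median that cannot be reached, and gives no between-arm estimate over total follow-up

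*SAP*

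**What the plan says.** A secondary safety objective in Protocol 8.2 is "To evaluate the long-term safety of lorcaserin HCl 10 mg BID". Protocol 9.5.1.5 states that "MACE and MACE+ events and other study-specific AEs of interest will be followed until EOS". Subjects who stop study drug stay in the study to completion (Protocol 9.5.5.1, SAP 3.3). Protocol 9.5.4.4 lists malignant neoplasms, "with the exception of basal cell and squamous cell carcinomas of the skin", among the study-specific events always reported as SAEs.

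For reporting, SAP 5.6.2 sets a general rule: "Only those AEs that were treatment emergent (including CEC adjudicated events) will be included in summary tables". The definition begins "A treatment-emergent AE (TEAE) is defined as an AE that emerges during treatment, having been absent at pretreatment (Baseline) or" and continues with re-emergence or worsening during treatment. It gives no period after the last dose. Incidence is the number and percentage of subjects in the Safety Analysis Set. Everything else goes to listings: "All AEs, treatment emergent or otherwise, will be presented in subject data listings".

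Events of interest have their own bullet: "The incidence of AEs of interest (Study Specific Events, see Section 9.5.4.4 of the protocol) will be summarized separately". It adds Kaplan-Meier curves, and "median time to first event and 95% CI will be presented".

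**The concern.** The trial collects events of interest through the whole of follow-up, but the general tabulation rule uses only the on-drug part. That matters most for harms with latency. A tumour may be diagnosed months after drug was stopped, and a subject may have stopped for reasons connected with it.

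Percentages of subjects with no person-time are also exposed to unequal stopping. If one arm leaves drug earlier, its count of on-treatment events falls while its denominator stays the same.

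MACE+, its components and all-cause mortality are analysed on the Total Time set, with on-treatment sets as sensitivity analyses. Malignancy has no such pair, no comparative estimate and no stated censoring rule. The one numerical time-to-event summary planned, the median, looks out of reach.

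**Working it through.** **1. Which events count.**
- The bullets in SAP 5.6.2 on deaths, SAEs and discontinuations each say treatment-emergent. The events-of-interest bullet does not.
- The general rule speaks of summary tables, and a Kaplan-Meier curve is a figure.
- The censoring rules in SAP 8.5 cover MACE, MACE+, mortality, conversion to diabetes, and the renal and glucose endpoints. None covers events of interest.

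So there are two readings. Either off-drug events are excluded by the general rule, or they are included with the numerator and censoring date left unstated. Both need a sentence in the SAP.

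**2. Can the median be reached?** With a constant hazard λ, cumulative incidence is 1 − exp(−λt) and the median is ln 2/λ.
- Hazard needed for a median by 54 months: 0.693/4.5 = 0.154 per year. By 56 months, the stated length of the Randomization Phase: 0.693/4.667 = 0.149.
- MACE+ at the planned 3.5% per year: 1 − exp(−0.035 × 4.5) = 14.6% at 54 months.
- Assumed event-of-interest rates of 0.5%, 1% and 2% per year give 2.2%, 4.4% and 8.6% at 54 months, with implied medians of 139, 69 and 35 years.

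**3. How many events could fall off drug?** The documents give neither a malignancy rate nor a drug-stopping rate, so this is an illustration.

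Inputs from SAP section 4: 12,000 subjects, 15-month uniform accrual, 54 months, 5% annual drop-out. Individual follow-up f therefore runs from 3.25 to 4.5 years.

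Check against the plan's own figures:
- The event formula gives 4 × (1.960 + 1.645)² / (ln 1.4)² = 459.2, so 460 events, as stated.
- The follow-up model gives 456 diabetes conversions against 457 stated, about 616 MACE at 54 months against approximately 600, 484 MACE at 43 months against 460, and 1,287 MACE+ (15% reduction) against 1401. It is good to within about 10%.

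Person-years = 12,000 × the average over f of (1 − exp(−d·f))/d, where d is the total exit hazard.
- All follow-up, d = 0.05: about 42,240.
- On drug, assumed stopping of 5% per year, d = 0.10: about 38,500 (91%).
- On drug, assumed stopping of 20% per year, d = 0.25: about 29,710 (70%).

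Off-drug person-years are therefore about 3,740 to 12,530. Events = rate × person-years, which slightly overstates first events.

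| Assumed malignancy rate | All follow-up | On drug | Off drug |
|---|---|---|---|
| 0.5% per year | 211 | 192 to 149 | 19 to 63 |
| 1% per year | 422 | 385 to 297 | 37 to 125 |
| 2% per year | 845 | 770 to 594 | 75 to 251 |

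**4. Precision.** At 1% per year, the 95% CI multiplies and divides the hazard ratio by exp(1.96 × 2/√events). That is 1.21 over all follow-up and 1.22 to 1.26 on drug. The gain in precision is modest. The case rests on latency and unequal stopping.

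**The case against.** Much of the plan already addresses long-term harm, and this limits the point.

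- A reader might infer that no event of interest has a between-arm estimate. That is not so. SAP 5.4.3 and 5.8 compare the arms on FDA-defined valvulopathy and pulmonary artery pressure, at 1 year and yearly from year 2, in ITT-based sets within the echo subset of about 3,600. The echo row in Protocol Table 4 does not carry the footnote that stops assessments after early discontinuation.
- A reader might infer that the median is the only summary. The same bullet plans incidence and Kaplan-Meier curves, and approximate yearly cumulative incidence can be read from the curves.
- A reader might infer that off-drug events are certainly dropped from the events-of-interest summary. For that bullet, the limit is inferred from the general rule.
- Symptoms that led a subject to stop drug arose on treatment and enter the discontinuation table. Only a later, separately recorded diagnosis falls outside. Fatal cancers count in all-cause mortality, analysed by Cox model on the Total Time set.
- Descriptive treatment-emergent tables follow Protocol 9.7.1.10, and the documents give no evidence of unequal stopping.

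All of this stands. It does not supply a numerator, a censoring rule or a comparative estimate for non-fatal malignancy, and it does not make the median informative.

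**Conclusion.** The point holds in a limited form. For malignancy, the SAP leaves open whether off-drug events count and how the curves are censored. It plans a median that cannot be estimated at any plausible rate, and it gives no comparative estimate over total follow-up. A reader might go further and infer that the long-term safety objective gets no usable answer. The documents do not support that: on-treatment incidence by arm in a randomised placebo comparison, the curves, the listings and total-time mortality are all usable.

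The median result needs only the planned study length and an approximately constant hazard. The 37 to 125 of about 422 events rest on an assumed 1% annual malignancy rate and assumed drug stopping of 5% to 20% per year. With constant hazard they would understate the loss if risk rises with latency or after stopping. The direction and size of any bias from unequal stopping cannot be judged from the documents.

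**What to change.** In SAP 5.6.2, for malignant neoplasms at least and for other Protocol 9.5.4.4 events as wanted:

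1. State whether events after permanent discontinuation count, and give the censoring date for the curves.
2. Tabulate first events from first dose to EOS regardless of drug status, beside the on-treatment table, with rates per 100 patient-years.
3. Replace the median with cumulative incidence by arm at each year.
4. Add a Cox hazard ratio with 95% CI (treatment and CV stratum, as in the other time-to-event models), censored at last contact. Label it descriptive, with no alpha.

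The cost is SAP wording and a few tables. The data are already collected, and neither conduct nor the testing hierarchy changes. The total-time table will include some off-drug events unrelated to drug, which is why the on-treatment table stays beside it.

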#### 5.6.3 Laboratory Values

Central Laboratory results will be summarized using Système International (SI) units, as appropriate. For all quantitative parameters listed in protocol Section 9.5.1.5 Safety Assessments (Laboratory Measurements), the actual value and the change from baseline to each postbaseline visit and to the EOT (defined as the last on-treatment value) will be summarized by visit and treatment group using descriptive statistics. Qualitative parameters listed in protocol Section 9.5.1.5 will be summarized using frequencies (number and percentage of subjects), and changes from baseline to each postbaseline visit and to EOT will be reported using shift tables. Percentages will be based on the number of subjects with both nonmissing baseline and relevant postbaseline results.

Laboratory test results will be assigned a low/normal/high (LNH) classification according to whether the value was below (L), within (N), or above (H) the laboratory parameter's reference

range. Within-treatment comparisons for each laboratory parameter will be based on 3-by-3 tables (shift tables) that compare the baseline LNH classification to the LNH classification at each postbaseline visit and at the EOT. Similar shift tables will also compare the baseline LNH classification to the LNH classification for the highest and lowest value during the treatment period.

Appendix 13.1 (Sponsor's Grading for Laboratory Values) presents the criteria that will be used to identify subjects with treatment-emergent markedly abnormal laboratory values (TEMAV). Except for phosphate, a TEMAV is defined as a postbaseline value with an increase from baseline to a grade of 2 or higher. For phosphate, a TEMAV was defined as a postbaseline value with an increase from baseline to a grade of 3 or higher. When displaying the incidence of TEMAVs, each subject may be counted once in the laboratory parameter high and in the laboratory parameter low categories, as applicable.

#### 5.6.4 Vital Signs

Descriptive statistics for vital signs parameters (i.e., diastolic and systolic BP, pulse, weight) and changes from Baseline will be presented by visit and treatment group. Descriptive statistics and changes from Baseline will also be presented by visit and treatment group for waist and hip circumference. In addition, systolic and diastolic blood pressure will be summarized by clinically notable changes (see Section 8).

#### 5.6.5 Electrocardiograms

Abnormal ECG findings will be presented as shifts from baseline (normal/abnormal clinically significant/abnormal not clinically significant) to post baseline (normal/abnormal clinically significant/abnormal not clinically significant) visits. The number and percent of subjects will be presented.

#### 5.7 OTHER ANALYSES

No other analyses are planned.

#### 5.8 EXPLORATORY ENDPOINT ANALYSES

• The change from Baseline in CV risk factors (body weight, BMI, waist and hip circumference, dyslipidemia, insulin level, hypertension, inflammatory biomarkers) will be analyzed using a mixed-effects model with repeated measures with treatment, month, month by treatment interaction and stratification variable (presence of established CV disease or CV risk factors without established CV disease) as factors and Baseline value as a covariate. Comparison between lorcaserin HCl and placebo will be made at 1year. The estimated treatment difference in the LSM between lorcaserin HCl and placebo, p-value, and the two-sided 95% CI will be calculated. The ITT will be used for this analysis. SAS PROC MIXED will be used using an unstructured covariance matrix (TYPE=UN). If the model fails to converge then other covariance structures such as; Heterogeneous Toeplitz covariance structure (TYPE= TOEPH), heterogeneous Autoregressive (TYPE=ARH(1)) or compound symmetry (TYP=CS) will be used.

- For subjects with NAFLD at Baseline, the change from Baseline in liver function tests (AST, ALT, alkaline phosphatase, GGT, total and direct bilirubin) will be analyzed using a mixed-effects model with repeated measures with treatment, month, month by treatment interaction and stratification variable (presence of established CV disease or CV risk factors without established CV disease) as factors and Baseline value as a covariate. Comparison between lorcaserin HCl and placebo will be made at 1 year. The estimated treatment difference in the LSM between lorcaserin HCl and placebo, p-value, and the two-sided 95% CI will be calculated. The ITT will be used for this analysis. SAS PROC MIXED will be used using an unstructured covariance matrix (TYPE=UN). If the model fails to converge then a Heterogeneous Toeplitz covariance structure (TYPE= TOEPH) will be used.
- The proportion of subjects who meet FDA-defined valvulopathy in echocardiographically determined heart valve changes will be analyzed using a logistic GLMM for repeated measures including treatment, month, month by treatment interaction as factors and baseline BMI as a covariate. Comparison between lorcaserin HCl and placebo will be made at 2 years and yearly thereafter. The odds ratio, p-value and 2-sided 95% CI will be calculated. The FDA-defined Valvulopathy Analysis Set will be used for this analysis.
- The change from baseline in eGFR and ACR will be analyzed using a mixed-effects model with repeated measures with treatment, month and month by treatment interaction as a factor and baseline value as a covariate. Comparison of the trajectories for lorcaserin HCl and placebo will be made at 1 year, yearly thereafter, and at EOS. The estimated treatment difference in the LSM between lorcaserin HCl and placebo, p-value, and the two-sided 95% CI will be calculated. The ITT will be used for this analysis. SAS PROC MIXED will be used using an unstructured covariance matrix (TYPE=UN). If the model fails to converge then a Heterogeneous Toeplitz covariance structure (TYPE=TOEPH) will be used.
- The change from Baseline in echocardiographically-determined pulmonary arterial systolic pressure will be analyzed using a mixed-effects model with repeated measures with treatment, month, month by treatment interaction as factors and baseline pulmonary arterial systolic pressure and baseline BMI as covariates. Comparison between lorcaserin HCl and placebo will be made at 2 years and yearly thereafter. The estimated treatment difference in the LSM between lorcaserin HCl and placebo, p-value, and the two-sided 95% CI will be calculated. The ITT will be used for this analysis. SAS PROC MIXED will be used using an unstructured covariance matrix (TYPE=UN). If the model fails to converge then a Heterogeneous Toeplitz covariance structure (TYPE= TOEPH) will be used.
- Change from Baseline in HbA1c, FPG, fasting insulin levels, and homeostatic model assessment insulin resistance (HOMA-IR), at 6 months in subjects with T2DM at Baseline will be analyzed using an ANCOVA model with treatment and stratification variable (presence of established CV disease or CV risk factors without established CV

disease) as factors, and baseline HbA1c, as a covariate. Comparison between lorcaserin HCl and placebo will be made at 6 months. The estimated treatment difference in the LSM between lorcaserin HCl and placebo, p-value, and the two-sided 95% CI will be calculated. The T2DM Analysis Set will be used for this analysis, in the following subpopulations.

- o Subjects with (HbA1c>7%) at Baseline
- o Subjects who have not been treated with antidiabetic agents at Baseline
- o Subjects who are on monotherapy with oral antidiabetic agent at Baseline
- Subjects with early T2DM (duration of diagnosis of diabetes is less than 5 years) at Baseline.
- Proportion of subjects with reduction in the number of OAD medications or reduction in the dosage of OAD medications in the following subpopulations of subjects with T2DM at Baseline will be analyzed using logistic regression including treatment as factor. Comparison between lorcaserin HCl and placebo will be made at 6 months. The odds ratio, p-value and 2-sided 95% CI will be calculated. The T2DM Analysis Set will be used for this analysis, in the following subpopulations:
  - o Subjects with (HbA1c > 7%) at Baseline
  - o Subjects who are on monotherapy with oral antidiabetic agent at Baseline
  - Subjects with early T2DM (duration of diagnosis of diabetes is less than 5 years) at Baseline
- Proportions of subjects with at least a 1-stage reduction in an obesity-related complication (prediabetes, metabolic syndrome, T2DM, hypertension, and hypertriglyceridemia/dyslipidemia), incidence of other obesity-related complications will be collected through AE reports, medical history, and use of concomitant medications, will be analyzed using logistic regression including treatment as factor. Comparison between lorcaserin HCl and placebo will be made at 1 year and EOS. The odds ratio, p-value and 2-sided 95% CI will be calculated. The ITT Analysis Set will be used for this analysis.

Logistic regression including treatment as factor will be used for the following endpoints. Comparison between lorcaserin HCl and placebo will be made at EOS. The odds ratio, p-value and 2-sided 95% CI will be calculated.

The Prediabetes Analysis Set will be used for the following analyses: (revised per Amendment 01)

- Proportions of subjects with prediabetes at Baseline who develop new diagnosis of diabetic retinopathy at EOS.
- Proportions of subjects with prediabetes at Baseline who develop new diagnosis of diabetic neuropathy at EOS.

The T2DM Analysis Set will be used for the following analyses: (revised per Amendment 01)

- Proportions of subjects with T2DM at Baseline who develop new diagnosis of diabetic retinopathy at EOS.
- Proportions of subjects with T2DM at Baseline who develop new diagnosis of diabetic neuropathy at EOS.

